5.3. Lifestyle Considerations

Throughout the study, participants may undergo medical assessments and review of compliance with requirements before continuing in the study.

5.3.1. Meals and Dietary Restrictions

Standard meals, according to the CRU SOPs, will be provided during the stay at the CRU. During the fasted dosing periods, participants will fast overnight for at least 8 hours prior to the morning dose and then fast for at least 4 hours after the morning dose. During the food-effect period, a standardized high-fat meal or a light breakfast will be provided at the CRU 30 minutes prior to dose administration following an overnight fast of at least 8 hours. During Part B on Days 1 and 5, participants will fast overnight for at least 8 hours prior to the morning dose and then fast for at least 4 hours after the morning dose. On days 2 through 4 participants can eat according to site procedure for non-fasted dosing. Unless otherwise instructed by CRU personnel, participants will maintain their own dietary habit throughout the ambulatory periods of the study.

5.3.2. Caffeine, Alcohol, and Tobacco

Participants will need to abstain from alcohol and caffeinated drinks from 48 hours prior to entry in the CRU until discharge.

Smoking outside the CRU should be restricted to 5 cigarettes a day or fewer during study participation.

5.3.3. Activity

Participants must refrain from new strenuous exercise routines 48 hours prior to each CRU confinement period and throughout their CRU stay.

5.4. Screen Failures

Screen failures are defined as participants who consent to participate in the clinical study but are not subsequently randomly assigned to study intervention.

Individuals who do not meet the criteria for participation in this study (screen failure) may be rescreened once at the discretion of the investigator with sponsor's approval. If a participant is rescreened, that participant would be assigned a new participant number and would need to sign a new ICF.

6. Study Intervention

Study intervention is defined as any investigational intervention(s), marketed product(s), placebo, or medical device(s) intended to be administered to/used by a study participant according to the study protocol.

6.1. Study Intervention(s) Administered

The study intervention, LY3526318, will be administered orally. Doses are planned to range between 100 mg and 1000 mg once daily (see Section 4.3, Dose Justification), and de-escalation is permitted.

Part A

The planned dose levels range from 100 mg to 1000 mg. LY3526318 or matching placebo will be administered to participants as a single dose by trained CRU personnel. Up to 3 single dose levels will be assessed in a fasted state (fasting at least 8 hours prior to and at least 4 hours after dosing). Up to two of these dose levels that were assessed in a fasted state will also be assessed in a fed state (a high-fat meal or a light breakfast 30 minutes prior to dosing). Dose levels may be modified based on safety and available PK but will not exceed the NOAEL.

Part B

The planned dose levels in Part B will not exceed those studied in Part A. After review of the data from Part A, Part B doses may be administered in a fed or fasted state or either on different days.

CCI

The placebo capsules will be identical in appearance to LY3526318 and are prepared extemporaneously. Placebo capsules will contain only microcrystalline cellulose.

LY3526318 and placebo capsules should be stored at 15°C to 30°C.

6.2. Preparation/Handling/Storage/Accountability

- Only participants enrolled in the study may receive study intervention, and only authorized site staff may supply or administer study intervention. All study intervention must be stored in a secure, environmentally controlled, monitored (manual or automated) area in accordance with the labeled storage conditions, with access limited to the investigator and authorized site staff.
- The investigator, institution, or the head of the medical institution (where applicable) is responsible for study intervention accountability, reconciliation, and record maintenance (ie, receipt, reconciliation, and final disposition records).

- Further guidance and information for the final disposition of unused study interventions are provided in the Pharmacy Manual. Note: in some cases, sites may destroy the study intervention if, during the investigative site selection, the evaluator has verified and documented that the site has appropriate facilities and written procedures to dispose of study intervention.

6.3. Measures to Minimize Bias: Randomization and Blinding

6.3.1. Method of Treatment Assignment

On Day 1 participants will be assigned a unique number (randomization number). Participants who meet all criteria for enrollment will be randomly assigned to receive either LY3526318 or placebo. A randomization table will be created using a computer software program. The randomization list will be provided to the designated unblinded CRU staff for participant randomization and dispensing purposes and kept in a secure location, accessible to the designated unblinded CRU staff only.

Participants, investigators, and CRU personnel performing trial-related activities or with the ability to influence study outcomes will be blinded with regards to LY3526318 and placebo treatment ([Figure 1.2](#)). To preserve the blinding of the sponsor, only a minimum number of Lilly personnel may have access to the randomization table and codes before the study is complete. Clinical research unit personnel who are responsible for participant-specific study intervention preparation will not be blinded; laboratory personnel, including bioanalytical laboratory personnel, will also not be blinded.

A sealed envelope that contains the study intervention assignment for each participant will be provided to the investigator. The investigator (or representative) will retain the sealed envelope in a secured area. In case of an emergency, the investigator has the sole responsibility for determining if unblinding of a participants' intervention assignment is warranted. Participant safety must always be the first consideration in making such a determination. If a participant's intervention assignment is unblinded, the sponsor must be notified immediately after breaking the blind. Once the study is complete, all envelopes (sealed and opened) must be inventoried and returned to the sponsor.

In the event of a quality assurance audit, the auditor(s) will be allowed access to unblinded study intervention records at the site to verify that randomization/dispensing has been done accurately.

If an investigator, site personnel performing assessments, or participant is unblinded, the participant must be discontinued from the study. In cases where there are ethical reasons to have the participant remain in the study, the investigator must obtain specific approval from a sponsor clinical research physician (CRP) for the participant to continue in the study.

6.3.2. Selection and Timing of Doses

All doses of the study intervention will be administered at the CRU approximately between 0800 hours and 1100 hours.

A trained CRU personnel member will administer all doses of the study intervention at the CRU.

6.4. Study Intervention Compliance

When participants are dosed at the site, they will receive study intervention directly from the investigator or designee, under medical supervision. The date and time of each dose administered in the clinic will be recorded in the electronic case report form (eCRF). The dose of study intervention and study participant identification will be confirmed at the time of dosing by a member of the study site staff other than the person administering the study intervention. Study site personnel will examine each participant's hands and mouth to ensure that the study intervention was ingested.

6.5. Concomitant Therapy

Drugs that are known inducers or inhibitors of CYP3A4 or 2C9 are to be specifically excluded (see Section 10.6, Appendix 6, for a list of excluded medications). Additional drugs are to be avoided during the study unless required to treat an AE or for the treatment of an ongoing medical problem.

Any medication or vaccine (including over the counter or prescription medicines, vitamins, and/or herbal supplements or other specific categories of interest) that the participant is receiving at the time of enrollment or receives during the study must be recorded along with

- reason for use
- dates of administration including start and end dates, and
- dosage information, including dose and frequency for concomitant therapy of special interest.

The medical monitor should be contacted if there are any questions regarding concomitant or prior therapy.

Participants must abstain from taking prescription or nonprescription drugs (including vitamins and dietary or herbal supplements) within 7 days (or 14 days if the drug is a potential enzyme inducer) or 5 half-lives (whichever is longer) before the start of study intervention until completion of the follow-up visit, unless, in the opinion of the investigator and sponsor, the medication will not interfere with the study.

Paracetamol, at doses of ≤ 2 grams/day, is permitted for use at any time during the study. Other concomitant medication may be considered on a case-by-case basis by the investigator in consultation with the medical monitor if required.

6.6. Dose Modification

6.6.1. Dose Escalation

The decision to proceed to the next dose level (either an increase or a decrease) will be made by the study team and the investigator based on safety, tolerability, and preliminary PK data obtained at the prior dose level.

By nature of being a dose escalation study, data will be evaluated on an ongoing basis until the mean LY3526318 exposure is projected to reach the NOAEL.

No dose decision can occur without prior discussion and agreement between the investigator and the sponsor's medical monitor.

In the SAD, the decision to escalate to the next dose will be based on vital signs, AEs, ECGs, and clinical laboratory assessments from predose to Day 4 from at least 4 individuals randomized to LY3526318. Pharmacokinetics data through at least 24 hours after the current dose will be used to inform the dose escalation decision.

Safety data, AEs, SAEs, and adverse laboratory abnormalities will be independently assessed by the investigator and will be considered related to the investigational product unless there is clear evidence that the event is not related.

After review of these data, the investigator and sponsor will make an agreement on the appropriate dose for the next cohort/dose level. The magnitude of dose escalations may be reduced following data review, but subsequent escalations cannot be increased by more than approximately 3-fold (a half-log increment). Doses lower than the initial dose of 100 mg may also be administered.

If any of the following scenarios occur, dosing at the current level and further dose escalation will be discontinued:

1. a single participant experiences a SAE or clinically significant event that is related to LY3526318 administration, or
2. if >3 participants at 1 dose level experience moderate treatment-related AEs that impair normal activities.

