10.3.3. Recording and Follow-Up of AE and/or SAE**AE and SAE Recording**

- When an AE/SAE occurs, it is the responsibility of the investigator to review all documentation (eg, hospital progress notes, laboratory reports, and diagnostics reports) related to the event.
- The investigator will then record all relevant AE/SAE information in the CRF.
- It is **not** acceptable for the investigator to send photocopies of the participant's medical records to the sponsor or designee in lieu of completion of the AE/SAE CRF page.
- There may be instances when copies of medical records for certain cases are requested by the sponsor or designee. In this case, all participant identifiers, with the exception of the participant number, **will be redacted** on the copies of the medical records before submission to the sponsor or designee.
- The investigator will attempt to establish a diagnosis of the event based on signs, symptoms, and/or other clinical information. Whenever possible, the diagnosis (not the individual signs/symptoms) will be documented as the AE/SAE.

Assessment of Intensity

The investigator will make an assessment of intensity for each AE and SAE reported during the study and assign it to one of the following categories:

- Mild - An event that is easily tolerated by the participant, causing minimal discomfort and not interfering with everyday activities.
- Moderate - An event that causes sufficient discomfort and interferes with normal everyday activities.
- Severe - An event that prevents normal everyday activities. An AE that is assessed as severe should not be confused with an SAE. Severe is a category utilized for rating the intensity of an event, and both AEs and SAEs can be assessed as severe.
 - An event is defined as ‘serious’ when it meets at least 1 of the predefined outcomes as described in the definition of an SAE, NOT when it is rated as severe.

Assessment of Causality

- The investigator is obligated to assess the relationship between study intervention and each occurrence of each AE/SAE.
- A “reasonable possibility” of a relationship conveys that there are facts, evidence, and/or arguments to suggest a causal relationship, rather than that a relationship cannot be ruled out.
- The investigator will use clinical judgment to determine the relationship.

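### Stopping criterion 2 counts moderate related AEs but not severe ones, so read literally a worse grade can lower the count towards a mandatory halt

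*Protocol*

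**What the plan says.** Protocol Section 6.6.1 (Dose Escalation) lists two scenarios. If either occurs, "dosing at the current level and further dose escalation will be discontinued".

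- Criterion 1: "a single participant experiences a SAE or clinically significant event that is related to LY3526318 administration".
- Criterion 2: "if >3 participants at 1 dose level experience moderate treatment-related AEs that impair normal activities".

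Section 10.3.3 has the investigator place every AE in one of three intensity categories. The two that matter here are "Moderate - An event that causes sufficient discomfort and interferes with normal everyday activities" and "Severe - An event that prevents normal everyday activities". It adds: "An AE that is assessed as severe should not be confused with an SAE".

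For causality in dose decisions, Section 6.6.1 presumes a relationship: an event "will be considered related to the investigational product unless there is clear evidence that the event is not related". The same section makes each dose decision depend on agreement between the investigator and the sponsor's medical monitor.

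The protocol does not define a clinically significant event. Sections 2.2 and 4.3 apply the term to adverse effects in earlier studies. Section 10.3.1 leaves it to the investigator's judgment for laboratory and other safety findings. Sections 7.1 and 8.2.3 use it for findings that prompt a decision about one participant. None of these ties it to an intensity grade.

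**The concern.** A mandatory stopping rule should be monotone in severity: if a set of events stops dosing, the same set with one event made worse should stop it too. Criterion 2 as printed lacks this property, because a severe AE is graded in a different category from the one being counted. Regrading an event from moderate to severe can therefore take a dose level from meeting the criterion to not meeting it.

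What is at stake is participant protection during escalation, not the analysis. These two scenarios are the only AE-based events that compel a halt; the other controls allow one without requiring it. The study has no Data Monitoring Committee (Section 9.6) and no sentinel dosing (Sections 1.1 and 2.1). Escalation may approach a mean AUC of 154 µg·h/mL, against 56 µg·h/mL at 100 mg in the earlier study. That is 154 / 56 = 2.75 times as high, so the mild TEAEs reported there give only partial reassurance.

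**Working it through.** The documents give no operating characteristic for the stopping rule, so there is no stated figure to reproduce. The check is a reading of the criteria against the grade definitions, followed by a count.

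**Inputs.** Each Part A period doses 8 participants, 2 of them on placebo (Protocol Section 1.2, sequence table), so 8 − 2 = 6 are active. Part B also has 6 active. The smallest number satisfying more than 3 is 4. Assume that all events are related and non-serious, and that each affected participant has events of one grade only. A participant with both a moderate and a severe AE would still be counted through the moderate one.

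**Rule.** Let m be the number of participants with a moderate related AE and s the number with a severe one.

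- Criterion 2 as printed is met when m ≥ 4.
- Criterion 2 counting moderate or severe is met when m + s ≥ 4.

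| m | s | As printed (m ≥ 4) | Moderate or severe (m + s ≥ 4) |
|---|---|---|---|
| 4 | 0 | met | met |
| 3 | 1 | not met | met |
| 2 | 2 | not met | met |
| 1 | 3 | not met | met |
| 0 | 4 | not met | met |
| 0 | 6 | not met | met |

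The first two rows show the reversal: regrading one of four moderate events as severe takes m from 4 to 3, and the criterion is no longer met.

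**Full enumeration for 6 active participants.** Pairs (m, s) with m + s equal to 4, 5 or 6 number 5 + 6 + 7 = 18. Those with m ≥ 4 number 3 + 2 + 1 = 6. So 18 − 6 = 12 patterns have at least four participants at moderate or worse yet do not meet criterion 2 as printed. These are counts of patterns, not probabilities, and no AE rate is assumed.

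**What criterion 1 does with those 12 patterns.** Each includes at least one severe event. The SAE limb does not apply, because severe is not serious. The remaining limb is met as soon as one severe event is judged clinically significant. The halt is therefore likely but rests on a judgment that the text does not link to the grade.

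**Dependence on the denominator.** The protocol does not say whether one dose level means one period or all periods at the same dose, and a blinded investigator sees 8 dosed participants rather than 6. Neither changes the result: as printed, criterion 2 counts no severe event whatever the denominator.

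**The case against.** The strongest reply is that the two criteria form two tiers. One event of real concern stops dosing; lesser events stop it by accumulation. On that reading a severe related AE is handled more strictly than a moderate one, with 1 participant needed instead of 4. An investigator would have to record that a healthy volunteer was prevented from normal activities, fail to rule out a drug relationship, and still call the event not clinically significant. Every severe event at the dose level would have to be treated that way. This is largely right, and it is why the gap is small in practice.

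Two further points have weight. The phrase about impairing normal activities can be read as a floor, since an event that prevents activities also impairs them, and moderate may have been meant as at least moderate. The text does not say so, and Section 10.3.3 defines the grades as separate categories. Next, escalation is not the default: "No dose decision can occur without prior discussion and agreement between the investigator and the sponsor", and Section 8 sends immediate safety concerns to the sponsor at once. These controls permit a halt but do not compel one.

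Three stronger readings are tempting and are not supported:

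- A reader might infer that severe AEs cannot stop the study. Criterion 1 can stop it after one participant.
- A reader might infer that a severe AE faces an additional hurdle compared with a moderate one. Criterion 1 requires no intensity grade; clinical significance takes the place of the grade and is not added to it. Intensity is itself an investigator assessment.
- A reader might infer that any single severe related AE must be made an automatic halt. That is debatable. The investigator is blinded, 2 of 8 participants per Part A period receive placebo, and events are presumed related, so a severe event on placebo could stop a dose level. Breaking the blind to check would normally remove that participant from the study (Section 6.3.1).

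**Conclusion.** The point holds as a wording defect in a safety rule. Criterion 2 as printed is not monotone in severity: 4 moderate related AEs meet it, while 3 moderate plus 1 severe, or 6 severe out of 6 active, do not. In those cases a mandatory halt rests on criterion 1, which will ordinarily be met but is not tied to the severe grade.

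The conclusion rests on taking moderate as the defined grade and not as shorthand for moderate or worse. If the sponsor meant the latter, the intent is sound and only the wording needs correction. The practical effect is small, for three reasons: a severe related AE is likely to be judged clinically significant, earlier TEAEs were mild (Section 2.1), and dose decisions need joint agreement. No PK or safety analysis is affected. The correction is still worth making, because it is cheap and concerns when dosing must stop.

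**What to change.** In Section 6.6.1, criterion 2, insert the words or severe after moderate, keeping the limit of more than 3 participants. Add one sentence saying that this does not limit criterion 1, under which a single clinically significant related event, as a severe AE will ordinarily be, still stops dosing. Without that sentence the new wording could be read as tolerating one to three severe AEs.

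With this change, regrading an event from moderate to severe can no longer lower the count. Where fewer than four participants are affected, a severe event still stops dosing only through criterion 1. The sponsor may choose to go further and name any severe related AE as a clinically significant event, accepting the risk of a halt caused by an event on placebo.

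The cost is a one-line protocol amendment, which needs IRB/IEC approval (Section 10.1.1), and the possibility of a slightly earlier halt. No new data are needed: intensity and causality are already assessed for every AE (Section 10.3.3), and SAP Section 17.1.1 already tabulates TEAEs by severity and relationship.

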6.7. Intervention after the End of the Study

Study intervention will not be made available after completion of the study to participants.

7. Discontinuation of Study Intervention and Participant Discontinuation/Withdrawal

Participants discontinuing from the study prematurely for any reason must complete AE and follow-up procedures per Section 1.3 of this protocol.

7.1. Discontinuation of Study Intervention

In rare instances, it may be necessary for a participant to permanently discontinue (definitive discontinuation) study intervention. If study intervention is definitively discontinued, the participant will remain in the study to be evaluated for early discontinuation procedures. See the SoA, Section 1.3, for data to be collected at the time of discontinuation of study intervention and follow-up and for any further evaluations that need to be completed.

Discontinuation due to a hepatic event or liver test abnormality:

Laboratory tests (Section 10.2, Appendix 2), including alanine aminotransferase (ALT), aspartate aminotransferase (AST), alkaline phosphatase (ALP), total bilirubin (TBL), direct bilirubin, gamma-glutamyl transferase (GGT), and creatine kinase (CK), should be repeated within 48 to 72 hours to confirm the abnormality and to determine if it is increasing or decreasing, if 1 or more of these conditions occur:

If a participant with baseline results of:	develops the following elevations:
ALT or AST <1.5x ULN	ALT or AST \geq 3x ULN
ALP <1.5x ULN	ALP \geq 2x ULN
TBL <1.5x ULN	TBL \geq 2x ULN (except for participants with Gilbert's syndrome)
ALT or AST \geq 1.5x ULN	ALT or AST \geq 2x baseline
ALP \geq 1.5x ULN	ALP \geq 2x baseline
TBL \geq 1.5x ULN	TBL \geq 2x baseline (except for participants with Gilbert's syndrome)

Abbreviations: ALP = alkaline phosphatase; ALT = alanine aminotransferase; AST = aspartate aminotransferase; TBL = total bilirubin; ULN = upper limit of normal.

If the abnormality persists or worsens, clinical and laboratory monitoring, and evaluation for possible causes of abnormal liver tests should be initiated by the investigator in consultation with the Lilly-designated medical monitor. At a minimum, this evaluation should include physical examination and a thorough medical history, including symptoms, recent illnesses (eg, heart failure, systemic infection, hypotension, or seizures), recent travel, history of concomitant medications (including over-the-counter), herbal and dietary supplements, and history of alcohol drinking and other substance abuse.

Initially, monitoring of symptoms and hepatic biochemical tests should be done at a frequency of 1 to 3 times weekly, based on the participant's clinical condition and hepatic biochemical tests. Subsequently, the frequency of monitoring may be lowered to once every 1 to 2 weeks, if the participant's clinical condition and lab results stabilize. Monitoring of ALT, AST, ALP, and TBL should continue until levels normalize or return to approximate baseline levels.

If a clinically significant finding is identified (including, but not limited to clinically significant changes from baseline in QTcF) after enrollment, the investigator or qualified designee will determine if the participant can continue in the study and if any change in participant management is needed. This review of the ECG printed at the time of collection must be documented. Any new clinically relevant finding should be reported as an AE.

If a participant becomes pregnant during the study, refer to Section [8.3.5](#).

See the SoA (Section [1.3](#)) for data to be collected at the time of intervention discontinuation and follow-up and for any further evaluations that need to be completed.

